6.3.3 Sample Collection Schedule

Blood will be collected for pharmacokinetic and pharmacodynamic analysis according to the schedule in **Table 2**. See section 10.1.1 for sample processing.

Table 2. Time Points of Blood Collection for PK Assessment after Phase 0 Microdose

Sample Number	Scheduled time points relative to ^{14}C Oxaliplatin administration		
	Day	Scheduled time	Description
1	1	0-5 min predose	Pre-dose
2	1	30 minutes (± 5 minutes)	Post-dose
3	1	1 hr (± 10 minutes)	Post-dose
4	1	1 hr 45 min (± 10 minutes)	Post-dose
5	1	2 hr (± 10 minutes)	Post-dose
6	1	2 hr 15 min (± 10 minutes)	Post-dose
7	1	3 hr (± 10 minutes)	Post-dose
8	1	4 hr (± 60 minutes)	Post-dose
9	1	24 hr (± 60 minutes)	Post-dose

6.4 Cycle 1 ^{14}C Oxaliplatin Microdose Concurrent with FOLFOX

6.4.1 Preparation and Administration of ^{14}C Oxaliplatin Microdose with Therapeutic Oxaliplatin dose.

The ^{14}C Oxaliplatin infusion mixture in D5W will be prepared as described in **Section 6.3.1**. After this infusion mixture is prepared, the shelf-life is 6 hours at room temperature [20-25 °C] or up to 24 hours under refrigeration [2-8 °C]. The treatment dose of oxaliplatin should also be prepared in a separate infusion bag containing D5W. Both treatment dose of unlabeled oxaliplatin and ^{14}C -labeled oxaliplatin will be concurrently infused intravenously over 2 hours at the UC Davis Cancer Center Infusion Center. A chemotherapy nurse will administer the unlabeled oxaliplatin. A Nuclear Medicine Technologist (CNMT) will administer the ^{14}C -labeled oxaliplatin via Y-site connection to the unlabeled oxaliplatin.

6.4.2 Sample Collection Schedule

Blood will be collected for pharmacokinetic and pharmacodynamic analysis according to the schedule in **Table 3**. See section 10.1.1 for sample processing.

Table 3. Time Points of Blood Collection for oxaliplatin PK Assessment after Therapeutic-Associated Microdose			
Sample Number	Scheduled time points relative to [¹⁴C]oxaliplatin administration		
	Day	Scheduled time	Description
1	1	0-5 min predose	Pre-dose
2	1	30 min (\pm 5 minutes)	Post-dose
3	1	1 hr (\pm 10 minutes)	Post-dose
4	1	1 hr 45 minutes (\pm 10 minutes)	Post-dose
5	1	2 hr (\pm 10 minutes)	Post-dose
6	1	2 hr 15 min (\pm 10 minutes)	Post-dose
7	1	3 hr (\pm 10 minutes)	Post-dose
8	1	4 hr (\pm 60 minutes)	Post-dose
9	1	24 hr (\pm 60 minutes)	Post-dose
10	2	48 hr (\pm two hours)	Post-dose

6.5 FOLFOX Treatment

6.5.1 Premedication and Supportive Care

Premedication associated with standard drug administration and supportive care (including anti-diarrheals, antibiotics, diuretics or other medications) should be given according to institutional standards.

6.5.2 FOLFOX

Patients will be treated with modified FOLFOX6 according to the following initial schedule for cycle 1. Cycle length is defined as 14 days. Modifications to cycle 1 treatment (other than oxaliplatin dose) may be allowed, but discussion with the primary investigator is required. Modifications to dosing beyond cycle 1 are at the discretion of the treating investigator according to usual medical practice.

Table 4. Modified FOLFOX6 Chemotherapy Regimen

Agent	Dose	Route	Day	Schedule
Leucovorin	400 mg/m ²	IV	1	Every 14 days
Calcium*				
5-FU	400 mg/m ²	Bolus IV	1	Every 14 days
Oxaliplatin	85 mg/m ²	IV over 2 hours	1	Every 14 days
5-FU	2400 mg/m ²	IV over 46-48 hours via ambulatory infusion pump	1-2	Every 14 days

*In the event of a leucovorin calcium shortage, the dosage may be reduced to 20 mg/m² or 200 mg/m² racemic levoleucovorin may be substituted. Leucovorin may be infused concurrently with oxaliplatin (via separate infusion lines).

** Note during cycle 1 only, Oxaliplatin infusion will contain [¹⁴C]Oxaliplatin Microdose as described in section 6.4.1

6.6 Follow Up Period

Patients will remain on study until progression of disease or until any of the criteria in **section 6.7** are met. If an intermittent oxaliplatin strategy is chosen, the time of progression will be defined as progression after the first reintroduction of oxaliplatin, as has previously been defined [79, 80].

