2.2 Oxaliplatin

Oxaliplatin is the third generation of platinum compounds approved for use in cancer therapy. It differs from cisplatin and carboplatin in two significant ways. First, oxaliplatin's toxicity profile shows a reduction in renal and auditory toxicities, and minimal myelosuppression. And second, it does not share the same resistance spectrum as of cisplatin and carboplatin. Oxaliplatin is active in many solid tumors, including colorectal, pancreatic, ovarian, lung, and head and neck carcinomas. Oxaliplatin is presently approved for use in combination with 5-fluorouracil (5-FU) and leucovorin (folic acid). This treatment regimen is indicated for (1) adjuvant treatment of stage III colon cancer in patients who have undergone complete resection of the primary tumor and (2) advanced colorectal cancer, (3) gastroesophageal adenocarcinoma, (4) pancreatic adenocarcinoma, (5) biliary adenocarcinoma, (6) appendiceal adenocarcinoma, (7) duodenal adenocarcinoma. At the present time, the most commonly used combination (modified FOLFOX6) combines oxaliplatin with bolus leucovorin and 5-FU followed by a 46-hour infusion of 5-FU [5, 6].

Oxaliplatin-associated toxicities are cumulative with dose received and are the most frequent cause of withdrawal from therapy for those patients that respond well to FOLFOX. The major dose limiting toxicity of oxaliplatin is neurotoxicity, which results in treatment interruption and discontinuation prior to disease progression in the majority of patients [7]. The predictability of neurotoxicity associated with oxaliplatin-based therapy should allow the development of strategies to manage this side effect in view of the individual patient's clinical situation. Variation of oxaliplatin in individual patients could affect the accumulation

of oxaliplatin with the nervous system as well as the disposition of oxalate. Thus, oxaliplatin dose optimization has the potential to reduce the development of neurotoxicity in patients treated with FOLFOX.

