6.7 Criteria for Discontinuation

Patients will be informed that they have the right to withdraw from the study at any time for any reason, without prejudice to their medical care. The investigator also has the right to withdraw patients from the study for any of the following reasons:

- Intercurrent illness
- Occurrence of an unacceptable adverse event
- A treatment delay between phase 0 microdose and FOLFOX treatment of greater than 28 days for any reason
- Patient request
- Protocol violations
- Non-compliance
- Administrative reasons
- Failure to return for follow-up
- General or specific changes in the patient's condition unacceptable for further treatment in the judgment of the investigator

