7.2 Adverse Events

Because the investigational intervention is not expected to result in any significant adverse events, adverse event evaluations will be performed at baseline, following each microdose administration, and for 14 days following microdose administration or until all attributed adverse events from the microdose have resolved, whichever is later. Adverse events will be graded accorded to the NCI Common Terminology Criteria for Adverse Events Version 4.0 (CTCAE v4.0). If CTCAE grading does not exist for an adverse event, the severity of mild, moderate, severe, and life-threatening, or grades 1 - 4, will be used. Upon completion of the adverse event assessment window, patients will be followed for efficacy only (see **section 7.3**) until the follow up criteria in **section 6.6** are met.

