8 CRITERIA FOR EVALUATION AND ENDPOINT DEFINITIONS

8.1 Criteria for Evaluation

Evaluable patients will include eligible subjects who receive both the phase 0 and FOLFOX-integrated microdose and have samples collected at least 80% of time points. All patients who receive any component of microdose will be followed for toxicity, but any patient not completing both microdose administrations and 80% of blood samples will be replaced.

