8.2.1.1 Justification of the primary endpoint

Prior microdosing work suggests that a close relationship between multiple microdose and full dose pharmacokinetic parameters including $t_{1/2}$ and AUC can be observed [77]. In this study, we have chosen to focus on total exposure to treatment as total exposure is related to the primary dose limiting toxicity of oxaliplatin treatment (i.e. peripheral neuropathy) [81]. While a close relationship will be required for final development, a relationship within 2-fold will provide sufficient preliminary data to suggest that further development and optimization of the assay will be warranted.

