SD	Non-CR/Non-PD/not evaluated	No	SD	documented at least once ≥ 4 wks. from baseline**
PD	Any	Yes or No	PD	no prior SD, PR or CR
Any	PD***	Yes or No	PD	
Any	Any	Yes	PD	

* See RECIST 1.1 manuscript for further details on what is evidence of a new lesion.
** Only for non-randomized trials with response as primary endpoint.
*** In exceptional circumstances, unequivocal progression in non-target lesions may be accepted as disease progression.

Note: Patients with a global deterioration of health status requiring discontinuation of treatment without objective evidence of disease progression at that time should be reported as "*symptomatic deterioration*." Every effort should be made to document the objective progression even after discontinuation of treatment.

For Patients with Non-Measurable Disease (i.e., Non-Target Disease)

Non-Target Lesions	New Lesions	Overall Response
CR	No	CR
Non-CR/non-PD	No	Non-CR/non-PD*
Not all evaluated	No	not evaluated
Unequivocal PD	Yes or No	PD
Any	Yes	PD

* 'Non-CR/non-PD' is preferred over 'stable disease' for non-target disease since SD is increasingly used as an endpoint for assessment of efficacy in some trials so to assign this category when no lesions can be measured is not advised

Duration of Response

Duration of overall response: The duration of overall response is measured from the time measurement criteria are met for CR or PR (whichever is first recorded) until the first date that recurrent or progressive disease is objectively documented (taking as reference for progressive disease the smallest measurements recorded since the treatment started).

The duration of overall CR is measured from the time measurement criteria are first met for CR until the first date that progressive disease is objectively documented.

Duration of stable disease: Stable disease is measured from the start of the treatment until the criteria for progression are met, taking as reference the smallest measurements recorded since the treatment started, including the baseline measurements.

Progression-Free Survival

Progression-free survival (PFS) is defined as the duration of time from start of treatment to time of progression or death, whichever occurs first.

Duration of Disease Control

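### Sections 6.6, 6.7 and 7.2 let progression and survival follow-up end before progression when a patient is withdrawn for toxicity, illness or non-compliance, which may truncate PFS and disease-control times informatively

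*Combined protocol and SAP*

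**What the plan says.** Section 6.6 sets the end of time on study: "Patients will remain on study until progression of disease or until any of the criteria in" Section 6.7 are met. Section 6.7 opens its list with "The investigator also has the right to withdraw patients from the study for any of the following reasons". The list includes "Occurrence of an unacceptable adverse event", intercurrent illness, protocol violations, non-compliance and a change in condition that the investigator judges incompatible with further treatment.

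Section 7.2 says that once the adverse-event window closes, "patients will be followed for efficacy only", and that this lasts until the Section 6.6 criteria are met. On toxicity, Section 8.1 says: "All patients who receive any component of microdose will be followed for toxicity".

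Section 11.2.2.3 defines PFS by radiographic progression or death from any cause. It builds duration of disease control (DDC) from PFS, adding the PFS after reintroduction when oxaliplatin is given intermittently. It states no censoring rule. The same section describes all secondary analyses as hypothesis generating.

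**The concern.** The Section 6.7 list removes a patient from the study, not only from treatment, and the plan does not separate the two. A patient withdrawn for toxicity or illness before progression then has no required progression date and no required survival status.

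Objective 1.2.3 relates adduct levels to response and PFS. The protocol's own premises suggest that such losses may not be random. Section 2.2 describes neurotoxicity as the main dose-limiting toxicity, "which results in treatment interruption and discontinuation prior to disease progression in the majority of patients". Section 8.2.1.1 adds that "total exposure is related to the primary dose limiting toxicity of oxaliplatin treatment". Section 2.6 states that adduct concentration follows drug concentration and incubation time in cell culture. If exposure influences both the adduct level and the chance of leaving follow-up, the adduct-outcome relation is estimated from times cut short for a reason tied to the marker. Progression dates that were never collected cannot be recovered at analysis.

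**Working it through.** The plan states no figure on this point, so the check is mainly a comparison of sections.

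**1. The chain of cross-references.** Section 7.2 ends efficacy follow-up by Section 6.6. Section 6.6 ends time on study at progression or when a Section 6.7 criterion is met. Section 6.7 includes health-related and conduct-related reasons. A patient who meets one of these without progression can therefore leave efficacy follow-up with neither PFS event observed.

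**2. Automatic or discretionary.** Section 6.6 turns on a criterion being met, which reads as automatic. Section 6.7 gives the investigator a right, which is discretionary. Two sites, or two investigators, could apply these sections differently to the same event.

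**3. Whether another section restores outcome follow-up.**

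- Section 9, footnote c, runs imaging until progression for patients with measurable disease. It does not say that this continues after withdrawal under Section 6.7.
- Appendix C says "Every effort should be made to document the objective progression even after discontinuation of treatment", but only in the note on symptomatic deterioration.
- Section 13.1 asks for vital status only from subjects who revoke authorization to use their health information.
- The Section 8.1 replacement rule covers missing microdoses and blood samples, not missing progression dates.

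None of these covers the general case.

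**4. Whether toxicity follow-up is affected.** Sections 7.1 and 7.2 run it for 14 days after a microdose or until attributed events resolve, whichever is later. Section 8.1 applies it to everyone given any microdose component. Section 11.2.2.4 runs it to at least 14 days after the second microdose or to recovery. Appendix C makes all patients evaluable for toxicity from the first microdose. Section 7.2 brings in Section 6.6 only after that window has closed. Toxicity follow-up therefore stands on its own.

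**5. Scale.** The input from the plan is n = 6 evaluable patients (Section 11.3). The withdrawal probability p before progression is not given, so 10%, 20% and 30% are assumed, with patients taken as independent.

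P(at least 1 lost) = 1 − (1 − p)^6, and P(at least 2 lost) = 1 − (1 − p)^6 − 6p(1 − p)^5.

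| Assumed p | At least 1 of 6 | At least 2 of 6 |
|---|---|---|
| 10% | 1 − 0.531 = 47% | 1 − 0.531 − 0.354 = 11% |
| 20% | 1 − 0.262 = 74% | 1 − 0.262 − 0.393 = 34% |
| 30% | 1 − 0.118 = 88% | 1 − 0.118 − 0.303 = 58% |

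To show how little six patients can spare, take the Pearson correlation needed for two-sided 5% significance, t/√(n − 2 + t²), where t is the 97.5% point on n − 2 degrees of freedom. It is 0.81 at n = 6, 0.88 at n = 5 and 0.95 at n = 4. The plan proposes no such test; the figures only show how fast information runs out.

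**The case against.** The case against giving this much weight is a fair one.

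- **The list is permissive.** Section 6.7 obliges no one to withdraw a patient, so a reader who infers that an adverse event always ends participation goes too far. This stands. Only the literal wording of Section 6.6 makes withdrawal automatic, and that mismatch is part of the point.
- **Safety data are not lost.** A reader might infer that a patient with an unacceptable adverse event drops out of safety follow-up before the event resolves. The documents do not support this, because the toxicity window is set independently of Section 6.6 (step 4 of the working).
- **The number lost is unknown.** A reader might infer from Section 2.2 that most of the six would be lost. That passage describes interrupting or stopping oxaliplatin, not leaving this study, and stopping oxaliplatin is not itself a Section 6.7 criterion. Section 6.6 and Appendix C provide for intermittent oxaliplatin and carry those patients through reintroduction. Loss would also require the toxicity to be judged unacceptable and, under Section 6.7, the investigator to choose withdrawal.
- **The informative mechanism is inferred.** Section 2.2 ties toxicity to cumulative dose, whereas adducts are measured only around the two microdose administrations. The documents give no relation between these adduct levels and withdrawal. The bias is possible, not demonstrated.
- **The stakes are limited.** The analysis is secondary and descriptive, in about six patients from several tumour sites. This stands, and it limits the weight of the point without removing the gap.

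**Conclusion.** The gap in efficacy follow-up is real. Read together, Sections 6.6, 6.7 and 7.2 allow, and on one literal reading require, outcome follow-up to end before progression for reasons connected with health or conduct. No section requires progression or survival follow-up afterwards, and Section 11.2.2.3 does not say how such a patient's time is handled.

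What is affected is the adduct-PFS/DDC analysis. The primary pharmacokinetic comparison is not, since patients without both microdoses and 80% of samples are replaced. The size of the problem cannot be read from the documents: the probabilities in the working rest on assumed withdrawal rates, and the suspicion of informative loss rests on the protocol's stated links between exposure, toxicity and adducts. The change is worth making because it is cheap and uncollected outcomes cannot be recovered. It is not a reason to doubt the study's main result.

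**What to change.** 1. Reconcile the automatic wording of Section 6.6 with the discretionary wording of Section 6.7.
2. State in Sections 6.6, 6.7 and 7.2 that meeting a Section 6.7 criterion does not by itself end data collection. The toxicity window of Sections 7.2, 8.1 and 11.2.2.4 continues. Progression follow-up (existing imaging schedule, for patients with measurable disease) and survival follow-up continue until progression or death, unless the patient withdraws consent or is lost to follow-up.
3. State in Section 11.2.2.3 that patients without a PFS or DDC event are censored at the last evaluable tumour assessment, and that the reason for censoring is reported for each.

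The amendment should leave untouched when or whether any treatment is stopped. In particular, it should not describe the Section 6.7 events as ending treatment, which would turn a discretionary list into a stopping rule.

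The cost is a wording amendment, longer follow-up of a few patients on scans already scheduled every 8 to 12 weeks, and vital-status checks.

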6.7 Criteria for Discontinuation

Patients will be informed that they have the right to withdraw from the study at any time for any reason, without prejudice to their medical care. The investigator also has the right to withdraw patients from the study for any of the following reasons:

- Intercurrent illness
- Occurrence of an unacceptable adverse event
- A treatment delay between phase 0 microdose and FOLFOX treatment of greater than 28 days for any reason
- Patient request
- Protocol violations
- Non-compliance
- Administrative reasons
- Failure to return for follow-up
- General or specific changes in the patient's condition unacceptable for further treatment in the judgment of the investigator

7 EVENTS TO BE MONITORED AND DOSE MODIFICATIONS

7.1 Safety Assessments

Safety will be monitored by performing a physical examination and assessing vital signs, performance status, laboratory evaluations, and collecting the adverse events. Because the investigational intervention is not expected to result in any significant toxicity, study safety evaluations will be performed at baseline, following each microdose administration, and for 14 days following microdose administration or until all attributed adverse events from the microdose have resolved, whichever is later. The timing of safety assessments after this period is at the discretion of the treating investigator according to good medical practice. For details on adverse event collection and reporting, refer to Section 7.2.

7.1.1 Physical Examination

A baseline comprehensive physical examination will be performed which must comprise a total body examination (general appearance, skin, neck, including thyroid, eyes, ears, nose, throat, lungs, heart, abdomen, back, lymph nodes, and extremity). A comprehensive physical examination will be performed at the Pre-Study visit and at the Cycle 2 - Day 1 study visit. A symptom-directed physical examination will be performed on the Cycle 1 - Day 1 study visit and at any time during the study, as clinically indicated.

7.1.2 Vital Signs

Vital sign assessment consists of height (pre-study visit only), pulse, blood pressure, respiration rate, temperature and weight. Blood pressure, pulse and respiration rate should be measured on patients after at least 3 minutes in the sitting position.

7.1.3 Performance Status

Zubrod (ECOG) Performance Status (**Appendix A**) will be determined by the treating Investigator at each physical examination visit.

7.1.4 Hematology

Hemoglobin, hematocrit, red blood cell count, white blood cell count with differential (neutrophils; lymphocytes; monocytes; eosinophils; basophils), and platelet count will be measured Pre-Study, on day 1 of Phase 0 Microdose, on Cycle 1 - Day 1, and Cycle 2 Day 1. Testing must be performed within 14 days of registration, and within 72 hours of subsequent time points.

7.1.5 Serum chemistry

Blood urea nitrogen (BUN), creatinine, total bilirubin, AST, ALT, alkaline phosphatase, sodium, potassium, chloride, calcium, glucose, total protein, and albumin, will be measured Pre-Study, on day 1 of Phase 0 Microdose, on Cycle 1 - Day 1, and Cycle 2 Day 1. Testing must be performed within 14 days of registration, and within 72 hours of subsequent time points.

7.1.6 Pregnancy Test

All pre-menopausal women who are not surgically sterile will have a urine pregnancy test at the Pre-Study visit and a urine pregnancy test as clinically indicated. A positive urine pregnancy test requires a serum β -hCG to be performed to confirm this result.

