4.2 Exclusion Criteria

- 4.2.1 Prior treatment with oxaliplatin.
- 4.2.2 Patients must not receive concomitant radiation.
- 4.2.3 Uncontrolled intercurrent illness including, but not limited to, ongoing or active infection, symptomatic congestive heart failure, unstable angina pectoris, cardiac arrhythmia, or psychiatric illness/social situations that would limit compliance with study requirements.

- 4.2.4 Participants who are pregnant or nursing.
- 4.2.5 Participants who are allergic to any platinum agent.
- 4.2.6 Participants who have more than Grade 1 peripheral neuropathy.

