6 STUDY DESIGN AND TREATMENT PLAN

6.1 Study Design

This is a prospective feasibility study of a [¹⁴C]oxaliplatin microdose assay to predict exposure and sensitivity to oxaliplatin as part of standard-of-care FOLFOX chemotherapy. Consenting patients who will be receiving FOLFOX as their treatment for cancer will be enrolled. Patients will receive two [¹⁴C]oxaliplatin microdose infusions over the course of the study. The first part of the study is a Phase 0 [¹⁴C]oxaliplatin microdose infusion occurring over 2 hours and followed by serial blood draws over a 24 hour period for microdose pharmacokinetic and pharmacodynamic analysis (on surrogate peripheral blood mononuclear cells). Between 2 days and 4 weeks after the administration of this phase 0 microdose, patients will begin FOLFOX therapy according to usual care. The initial treatment oxaliplatin dose will be diluted with the same amount of [¹⁴C]oxaliplatin microdose as previously administered. Repeat blood draws for pharmacokinetic assessment of both the microdose and therapeutic dose along with pharmacodynamic analysis on PBMCs will be performed over 46-48 hours (this last draw is timed for the disconnect visit of the 5-FU infusion).

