9 STUDY CALENDAR

PERIOD	Pre-Study ^a	Phase 0 Microdose		Cycle 1 + Microdose			Ongoing Treatment		Off Study
		Day 1	Day 2	Day 1	Day 2	Day 3	Cycle 2, Day 1	Ongoing Treatment	
Safety Assessments.^b See Section 7.1									
History & Physical Exam	X			X			X	*	
Vital Signs	X	X		X			X	*	
Performance Status	X			X			X		
Hematology	X	X		X			X	*	
Serum Chemistries	X	X		X			X	*	
Pregnancy Test	X								
Adverse Events. See Section 7.2									
Adverse Events		X-----X							
Efficacy Assessments. See Section 7.3									
Imaging Studies	X						X ^c	X	
Treatments. See Section 6.									
[¹⁴ C]Oxaliplatin Microdose		X		X					
FOLFOX				X-----X			X	*	
Biologic Agent, if appropriate						X		*	
Correlative Studies. See Sections 6.3.3, 6.4.2 and 10.1									
Plasma Pharmacokinetics		X	X	X	X	X			
PBMCs		X	X	X	X	X			

^a Pre-study assessments within 14 days before registration, except for imaging studies within 28 days of registration

^b All on study safety assessments may be performed +/- 72 hours of the indicated timepoint

^c Every 8 weeks (+/- 1 week) for 6 months then every 12 weeks (+/- 2 weeks) until progression. Required only in patients with measurable disease at baseline.

* After Cycle 2, Day 1 and resolution of all microdose-associated toxicities, all safety assessments and treatments are at the discretion of the treating investigator according to good medical practice.

[figure not shown]

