All measurements should be taken and recorded in metric notation using a ruler or calipers. All baseline evaluations should be performed as closely as possible to the beginning of treatment and never more than 4 weeks before the beginning of the treatment.

The same method of assessment and the same technique should be used to characterize each identified and reported lesion at baseline and during follow-up. Imaging-based evaluation is preferred to evaluation by clinical examination unless the lesion(s) being followed cannot be imaged but are assessable by clinical exam.

Clinical lesions: Clinical lesions will only be considered measurable when they are superficial (e.g., skin nodules and palpable lymph nodes) and ≥ 10 mm diameter as assessed using calipers (e.g., skin nodules). In the case of skin lesions, documentation by color photography, including a ruler to estimate the size of the lesion, is recommended.

Chest x-ray: Lesions on chest x-ray are acceptable as measurable lesions when they are clearly defined and surrounded by aerated lung. However, CT is preferable.

Conventional CT and MRI: This guideline has defined measurability of lesions on CT scan based on the assumption that CT slice thickness is 5 mm or less. If CT scans have slice thickness greater than 5 mm, the minimum size for a measurable lesion should be twice the slice thickness. MRI is also acceptable in certain situations (e.g. for body scans).

Use of MRI remains a complex issue. MRI has excellent contrast, spatial, and temporal resolution; however, there are many image acquisition variables involved in MRI, which greatly impact image quality, lesion conspicuity, and measurement. Furthermore, the availability of MRI is variable globally. As with CT, if an MRI is performed, the technical specifications of the scanning sequences used should be optimized for the evaluation of the type and site of disease. Furthermore, as with CT, the modality used at follow-up should be the same as was used at baseline and the lesions should be measured/assessed on the same pulse sequence. It is beyond the scope of the RECIST guidelines to prescribe specific MRI pulse sequence parameters for all scanners, body parts, and diseases. Ideally, the same type of scanner should be used and the image acquisition protocol should be followed as closely as possible to prior scans. Body scans should be performed with breath-hold scanning techniques, if possible.

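### The only required pregnancy test can be 14 days old at phase 0 and 42 days old at full-dose cycle 1, and no repeat is required before either infusion

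*Combined protocol and SAP*

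**What the plan says.** Pregnancy is an exclusion: section 4.2.4 bars "Participants who are pregnant or nursing". Section 4.1.10 asks for one negative pre-study test, and section 4.1.11 asks women of child-bearing potential to agree to contraception.

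On testing, section 7.1.6 states that women who are pre-menopausal and not surgically sterilised "will have a urine pregnancy test at the Pre-Study visit and a urine pregnancy test as clinically indicated", and that a positive urine result must be confirmed in serum. The section 9 calendar marks the test in the Pre-Study column only. Its footnote a sets the window: "Pre-study assessments within 14 days before registration, except for imaging studies within 28 days of registration".

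On timing, section 6.1 states: "Between 2 days and 4 weeks after the administration of this phase 0 microdose, patients will begin FOLFOX therapy according to usual care". Section 6.7 lists a longer delay among the reasons for which the investigator may withdraw a patient.

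Other laboratory tests are handled differently. Section 7.1.5 states that chemistry "will be measured Pre-Study, on day 1 of Phase 0 Microdose, on Cycle 1 - Day 1, and Cycle 2 Day 1", and section 7.1.4 gives the same schedule for haematology, with the rule "Testing must be performed within 14 days of registration, and within 72 hours of subsequent time points".

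**The concern.** The test supports an absolute exclusion, but it is tied to registration and not to dosing. The design then puts a phase 0 infusion and up to four weeks between eligibility and chemotherapy, so the result ages before the exposure that matters most. Blood counts and chemistry are refreshed at both infusion visits; pregnancy status is not.

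The stake is fetal safety. A woman who conceives after the Pre-Study test meets no further required pregnancy test before she receives cycle 1. Sections 3.2.1 and 3.2.3 list 5-FU and oxaliplatin as category D, and section 3.2.3 reports developmental mortality in animals at under one-tenth of the recommended human oxaliplatin dose. Most of the risk is therefore at cycle 1. Phase 0 gives about 1% of the oxaliplatin dose (3% at dose levels 2 and 3), and the documents give no fetal-harm figure at that level.

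The sections agree with one another, so this is not an inconsistency. The question is whether the stated rule is a strong enough safeguard.

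**Working it through.** The protocol states no test age of its own, so there is no figure to reproduce. The ages follow from adding its time windows.

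**Inputs**
- Pre-Study test to registration: 0 to 14 days (section 9, footnote a).
- Registration to phase 0, called *g*: no direct limit found. It is set to 0 for the main figures; this is an assumption.
- Phase 0 to FOLFOX cycle 1, called *d*: 2 to 28 days (section 6.1; section 6.7 for the upper end).

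**Formulas for the oldest permitted test**
- At phase 0: 14 + *g*
- At cycle 1: 14 + *g* + *d*

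**Main result, *g* = 0**
- Phase 0: youngest 0 days, oldest 14 days.
- Cycle 1: youngest 0 + 2 = 2 days, oldest 14 + 28 = 42 days.

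**If there is a registration gap** (illustrative values, *d* = 28)
- *g* = 7: 21 days at phase 0 and 49 days at cycle 1.
- *g* = 14: 28 days and 56 days.

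**Possible indirect limit.** Appendix C says baseline tumour evaluations should be "never more than 4 weeks before the beginning of the treatment". Section 7.3 places screening imaging before registration, so if this rule applies, registration can be at most 28 days before treatment. It does not say which infusion counts as treatment:
- If FOLFOX: oldest test at cycle 1 = 14 + 28 = 42 days, and at phase 0 = 42 − 2 = 40 days.
- If phase 0: oldest test at phase 0 = 14 + 28 = 42 days, and at cycle 1 = 42 + 28 = 70 days.

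The rule is about tumour measurement, and it may not apply to patients without measurable disease. The main result does not rest on it.

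**Dose at each infusion.** In the worked example of section 6.3.1, total oxaliplatin is 1.58 mg at phase 0 against a therapeutic dose of 158 mg at cycle 1: 1.58 / 158 = 1%.

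**Under the proposed rule.** 72 hours = 3 days, at both infusions.

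**The case against.** The strongest reply is that the protocol has a coherent rule and this review simply prefers a stricter one. Entry requires a negative test and agreed contraception, retesting is available whenever there is clinical reason, and a positive result is confirmed in serum. FOLFOX is standard treatment that these patients were going to receive anyway, so its fetal risk is largely a matter for usual practice. The calendar also requires a history and physical examination at Cycle 1 Day 1, which could prompt a test. The haematology and chemistry repeats are monitoring bloods: nothing makes them a condition for dosing, and footnote b of the calendar ("All on study safety assessments may be performed +/- 72 hours of the indicated timepoint") would let them be drawn after the infusion. Finally, very few women are likely to be affected.

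Much of this stands, and it limits the weight of the point. The comparison with routine bloods shows that the protocol refreshes other safety data at these visits; it does not show that the protocol has a pre-dose check for them. The Cycle 1 examination is a real contact, but it is symptom-directed, it has no counterpart in the calendar at phase 0, and it relies on someone suspecting pregnancy. Small numbers limit how often harm could occur, not how serious it would be.

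The objection does not remove the gap. Contraception is an agreement, and at entry the protocol does not rely on it alone but also requires a negative test. Cycle 1 is also more than usual care: the protocol specifies its regimen, adds an investigational labelled infusion and mandates its bloods. Nothing in the documents says that usual care will supply a pregnancy test.

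**Conclusion.** The concern holds. One urine test at Pre-Study is the only one required, and it may be 14 days old at phase 0 and 42 days old at cycle 1. These figures assume that phase 0 falls on the day of registration and that the 28-day interval is respected. Neither is firm. No direct limit on the registration gap is stated, and a longer delay before FOLFOX gives the investigator a right to withdraw the patient without an automatic stop. The true age could therefore be greater.

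The reach is small. Only women who are pre-menopausal and not surgically sterilised are affected, in a study planned for 6 evaluable patients, and the documents do not show how many such women will enrol. There is no effect on the sample size or the primary analysis. This is a safety improvement that should be made because the possible harm is serious and the remedy is cheap.

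**What to change.** In section 7.1.6, require a negative urine pregnancy test within 72 hours before the Phase 0 Day 1 infusion, and again within 72 hours before the Cycle 1 Day 1 infusion, for the women that section already covers. Mark both visits in the pregnancy-test row of the calendar.

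The word *before* has to be written out. Footnote b lets on-study safety assessments fall up to 72 hours either side of the time point, so a calendar mark alone would allow a test after dosing.

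The cost is one sentence, two marks in an existing row, and at most two extra urine tests per affected woman at visits where blood is already tested. If only one repeat is accepted, choose Cycle 1 Day 1: the dose is full there and the Pre-Study result is older.
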